#### **Methods for primary analysis**

The study will be declared positive if the median PFS of radium-223 in total sample is

EudraCT number: 2016-001888-36

statistically significantly better compared with null hypothesis (PFS  $\leq$  3 months;  $p < 0.05$ ).

The analysis will be based on the maximum-likelihood for exponential distribution test.

Additionally, the PFS will be analyzed with Kaplan Meier method in all patients and in both cohorts. We will provide the number and proportion of events and median survival time with corresponding 95% CI.

The primary analysis will be conducted on the full analysis set. The analysis in per protocol set will be considered as supportive.

## 7.2 Secondary analysis

All efficacy endpoints will be described in both study cohorts (AR-V7-negative and positive) and combining both cohorts.

All efficacy endpoints will be evaluated at the first 34 months period of the study. Additionally, OS will be evaluated at the 2-years safety extension after the end of the treatment. The other efficacy endpoints will not be evaluated at the 2-years safety extension.

All secondary analyses will be based on the full analysis and per protocol sets.

### 7.2.1 Summary statistics

#### Efficacy:

- OS is defined as the time from inclusion until death from any cause or the last date the patient was known to be alive. Patients who are lost to follow-up and the patients who are alive at the date of data cut-off are censored at the date the patient was last known alive (censoring rules are specified in
  - Appendix I). The OS will be assessed by cohorts.
- Time to first SSE is defined as the time from treatment initiation until SSE (pathological fractures, vertebral or non-vertebral, spinal cord compression, radiation or surgery to bone). For all other events, the start date of the event/medication/therapy was used as the time of the event. If an event has not occurred at the time of the analysis or the patient has been lost to follow-up, the time-to-event variables will be censored at the last disease assessment date.
- The time from the first study drug administration to when PSA progression was observed, defined as:
  - 1) In subjects with no PSA decline from baseline:  
a greater than or equal to 25% increase from baseline value and an increase in absolute value of greater than or equal to 2 ng/mL, at least 12 weeks from baseline;
  - 2) In subjects with initial PSA decline from baseline:

the time from start of treatment to first PSA increase that is greater than or equal to 25% increase and at least 2 ng/mL above the nadir value, which was confirmed by a second value obtained three or more weeks later.

- Determination percentage of PSA progression (defined as PSA elevation  $\geq 25\%$  and  $\geq 2$  ng/mL after 12 weeks).
- Alkaline phosphatase (AF) level response, normalization of alkaline phosphatase level (progression defined as AF elevation  $\geq 25\%$  after 12 weeks). The patients will be classified according on whether there is AF progression or not.
- Radiographic progression-free survival (rPFS) depending on AR-V7 status.

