5. STUDY ASSESSMENTS AND PROCEDURES

5.1. Screening phase: Patient enrollment procedures

Study-specific assessments performed during the screening phase: From Day 0 (patient allocation) to day 28 (to confirm remaining screening criteria during days 1-28 after day 0 of the screening phase).

Written informed consent from the patient must be signed before performing any study procedure (before screening assessment). By giving their consent, patients will be informed as to the nature of the study drug and will receive pertinent information regarding the study objectives, possible benefits, and potential AEs. They will also receive information on the follow-up procedures and

possible risks they will be exposed to. This document also informs patients about how biological samples will be obtained and collected and its legal implications. After receiving the document, the patient will read it (or receive information verbally before witnesses) and will sign the previously approved informed consent. The patient will receive a signed copy of the informed consent. The patient can withdraw their consent and discontinue the study, this will not affect any future medical treatment.

At inclusion:

1. The Sponsor will request the patient's demographic and clinical data related to screening criteria.
2. Each patient will be given a Unique Patient Number (UPN) for this study, provided by the Sponsor. All data will be recorded in the appropriate CRF using this identification number. This number will be provided to the central laboratory to ensure traceability of study samples.

Confirmation of patient's eligibility for study participation will be recorded in the CRF. The investigator is responsible for safeguarding patient information (e.g., age, name, address, telephone number, social security number, and study identification number), ensuring access to this information by Health Authorities if necessary. These records will remain confidential for the period of time stipulated by current legislation.

The following will be obtained during the screening phase:

- Anamnesis, medical history, and assessment of symptoms.
- Physical examination and measurement of height, weight, vital signs, and performance status.

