8.3.2. Secondary endpoints

All efficacy endpoints will be described in both study cohorts (AR-V7-negative and positive) and combining both cohorts.

All efficacy endpoints will be evaluated at the first 34 months period of the study. Additionally, OS will be evaluated at the 2-years safety extension after the end of the treatment. The other efficacy endpoints will not be evaluated at the 2-years safety extension.

-OS defined as the time from inclusion until death from any cause or the last date the patient was known to be alive.

Patients who are lost to follow-up and the patients who are alive at the date of data cut-off are censored at the date the patient was last known alive. Censoring rules are specified in **Table 3**.

- Time to first SSE defined as the time from treatment initiation until SSE (pathological fractures, vertebral or non-vertebral, spinal cord compression, radiation or surgery to bone). For all other events, the start date of the event/medication/therapy was used as the time of the event. If an event has not occurred at the time of the analysis or the patient has been lost to follow-up, the time-to-event variables will be censored at the last disease assessment date.

- Alkaline phosphatase level response, normalization of alkaline phosphatase level(progression defined as FAelevation \geq 25% after 12 weeks).

- The time from the first study drug administration to when PSA progression was observed, defined as: 1) In subjects with no PSA decline from baseline; a greater than or equal to 25% increase from baseline value and an increase in absolute value of greater than or equal to 2 ng/mL, at least 12 weeks from baseline; 2) In subjects with initial PSA decline from baseline; the time from start of treatment to first PSA increase that is greater than or equal to 25% increase and at least 2 ng/mL above the nadir value, which was confirmed by a second value obtained three or more weeks later.

- Determination percentage of PSA progression(defined as PSA elevation \geq 25% and \geq 2 ng/mL after 12 weeks).

-Radiographic progression-free survival (rPFS) depending on AR-V7 status

Predictive biomarkers

- Assessment of AR-V7 mutation prior to the start of study treatment and at time to documented progression disease or treatment end (see Appendix 3).

-Determination changes in CTCs number prior to the start of study treatment and at time to documented progression disease or treatment end (see Appendix 3).

Table 3. Censoring rules for OS

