## **6. Analysis sets**

### Full analysis set

All patients that accomplish selection criteria and receive at least one dose of study medication.

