### Per protocol set (PP)

All patients that accomplished selection criteria, received the study drug according to protocol timelines and dosing, and had no major protocol deviations. Criteria for determining the PP group assignment would be established by the Steering Committee before the statistical analysis begins. Patients without AR-V7 status in the study will be excluded.

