## 7.5 ***Transformation of expected variables***

- The time to progression is defined as the difference between start of drug (C1D1) and the progression date or death (whichever occurs first) or the last radiological assessment documented.
- The time to death is defined as the difference between the time from inclusion and death.
- The time to first SSE is defined as the difference between start of drug and the first symptomatic skeletal symptom.

EudraCT number: 2016-001888-36

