### **8.5 Handling of missing data**

For time-to-event endpoints, patients without a date of disease progression will be analyzed as censored observations on the date of last tumor assessment. If no post-baseline tumor assessment is available, patients will be censored at the date of first treatment + 1 day. Data for patients with an event (progression) who missed two or more scheduled assessments immediately prior to the event will be censored at the last tumor assessment prior to the missed visits.

For OS, patients who are not reported as having died will be analyzed as censored observations on the date they were last known to be alive. If no post-baseline data are available, OS will be censored at the date of treatment + 1 day.

EudraCT number: 2016-001888-36

For objective response and clinical benefit, patients without any post-baseline assessment will be considered non-responders.

For patients with AR-V7 status not available at baseline, we will assume the AR-V7 status provided at end of treatment or progression, whichever occurs first. Patients with AR-V7 status not available in the study will be considered as AR-V7 negative.

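### OS is counted from inclusion but analysed only in treated patients, so any gap between inclusion and first dose is guaranteed survival time

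*SAP*

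**What the plan says.** **Origin of OS.** Three places give the same start. Protocol 8.3.2: "OS defined as the time from inclusion until death from any cause". SAP 7.2.1: "OS is defined as the time from inclusion until death from any cause". The derivation rule in SAP 7.5: "The time to death is defined as the difference between the time from inclusion and death".

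**Patients in whom OS is analysed.** SAP 7.2: "All secondary analyses will be based on the full analysis and per protocol sets". SAP 6 defines the full analysis set as "All patients that accomplish selection criteria and receive at least one dose of study medication". The per protocol set is limited to eligible patients who "received the study drug according to protocol timelines and dosing, and had no major protocol deviations". Protocol 8.3.3 also requires a drug exposure.

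**Origin of the other time-to-event endpoints.** PFS starts with radium-223 treatment (protocol 8.3.1, SAP 7.1.1), which SAP 7.5 identifies as C1D1. Time to first skeletal event and time to PSA progression also start at first treatment (protocol 8.3.2, SAP 7.2.1).

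**Timing of inclusion.** No date is defined. Protocol 5.1 lists the steps at inclusion under the screening phase and describes that phase as running "From Day 0 (patient allocation) to day 28". Appendix 1 places screening on days −28 to −1. Protocol 6.1 puts treatment after enrolment.

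**The concern.** Entry to the OS analysis depends on something that happens after the OS clock has started. To be analysed, a patient must live long enough to be dosed, yet the time before the dose counts towards his survival. Within the analysed sets the risk of death over that interval is zero by construction.

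SAP 6.1 foresees patients who complete screening but are never given the drug, so the selection is not purely theoretical. Neither document corrects for it: there is no delayed entry at first dose and no OS analysis of everyone included.

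The direction is known, because any non-zero gap makes OS look longer. In a single-arm trial the Kaplan-Meier median OS is a figure that readers will set against outside results. OS is also the one efficacy endpoint carried into the two-year extension. Finally, because inclusion has no defined date, two programmers could derive different OS times from the same data.

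**Working it through.** **1. The plan's own figure.** No OS assumption, threshold or power is stated. The only sizing figure is N = 52 for PFS, and it reproduces. Inputs from protocol 8.2: median PFS 3 against 6.3 months, one-sided alpha 0.05, power 80%, 23 months of accrual plus 11 of follow-up, 25% AR-V7-positive.

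- Events (exponential test, log scale) = ((1.645 + 0.842) / ln(6.3/3))² = 11.23.
- P(event) under the target = 1 − (e^(−11λ) − e^(−34λ)) / (23λ), with λ = ln 2 / 6.3. This gives 0.892.
- AR-V7-positive patients = 11.23 / 0.892 = 12.6, rounded up to 13. Total = 13 / 0.25 = 52.

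This calculation uses only PFS, which already starts at first dose. The origin of OS does not enter it.

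**2. Effect of the origin.** For a treated patient, OS from inclusion = G + OS from first dose, where G is the time from inclusion to first dose. Nobody in the analysed sets can die during G. If G is the same for all, the Kaplan-Meier curve moves right by G and the median rises by exactly G.

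**3. Range of G.** The lower limit is 0 (inclusion and dosing on the same day). The upper limit is about 28 days, from the screening window in protocol 5.1 and Appendix 1. In months: 28 / 30.4375 = 0.92.

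**4. Scale.** The 14.9-month median comes from the updated pivotal-trial analysis in protocol 1.2. It is an assumption for scale only.

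| G | Rise in median OS | Share of 14.9 months |
|---|---|---|
| 0 days | 0 | 0% |
| 7 days | 0.23 month | 1.5% |
| 14 days | 0.46 month | 3.1% |
| 28 days | 0.92 month | 6.2% |

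With gaps spread evenly over 0 to 28 days (mean 14 days), simulated exponential survival gave a median of 15.36 months from inclusion against 14.89 from first dose, a difference of 0.47 month. The documents give no distribution for the gap, so this is an illustration.

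The relative ceiling depends on the reference median. It is 0.92 / 11.3 = 8.1% for the pivotal trial's placebo arm, and 0.92 / 30.2 = 3.0% for the placebo arm of the enzalutamide trial in patients without prior docetaxel (protocol 1.1).

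**5. AR-V7 comparison.** Both cohorts share one origin. A common G leaves the order of survival times unchanged, and with it the log-rank and Cox results. A bias would need G to differ between cohorts. AR-V7 is determined retrospectively after inclusion (protocol 8.2), so its result cannot set the gap.

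**The case against.** The strongest reply is that the gap may hardly exist. Protocol 4.2 has eligibility documented before enrolment, SAP 8.3 counts screening failures separately from enrolled patients, and protocol 6.1 moves from enrolment to treatment. If inclusion means enrolment after screening, the 28 days separate consent from dosing, and G could be a few days or zero. This stands. It rules out saying that every OS time contains a pre-dose stretch, and it rules out any lower bound above zero. It does not remove the mismatch, because the inclusion date is undefined and protocol 5.1 places inclusion within screening.

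A second reply is that bias depends on the target. Against OS from first dose, the effect is an offset of G. Against OS from inclusion in all included patients, the distortion comes from those left out because they were never dosed. Early deaths among them should be few, since protocol 4.2 asks for asymptomatic disease, ECOG 0–1 and a life expectancy of at least 12 months. A constant hazard with a 14.9-month median would give 52 × (1 − e^(−0.693 × 0.92 / 14.9)) = 2.2 deaths in 28 days. That hazard comes from a different population and should not be relied on here. This reply also stands as a limit on size; either way the chosen origin does not match the chosen set.

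Two stronger readings are tempting, and the documents do not support them:

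- A reader might infer from SAP 8.5 that OS has a second, conflicting origin, because for patients without post-baseline data "OS will be censored at the date of treatment + 1 day". That rule fixes the date on which follow-up ends. The time from inclusion to that date is well defined, so there is no contradiction.
- A reader might infer that PFS and OS cannot be interpreted together. An offset of at most 0.92 month does not make two Kaplan-Meier summaries unreadable side by side.

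**Conclusion.** The point holds as a small one. OS starts at inclusion but is analysed only in treated patients, so any interval between inclusion and first dose is immortal time that lengthens OS. The size is 0 to 0.92 month, or 0 to 6% of a 14.9-month median. This rests on two assumptions: that the 28-day screening window bounds the gap, and that the pivotal-trial median serves for scale, although this trial enrols asymptomatic patients and states no expected OS.

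OS is a secondary endpoint described by Kaplan-Meier, with no threshold or decision rule. The primary PFS test and N = 52 are unaffected, and the AR-V7 comparison is affected only if the gap differs between cohorts.

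**What to change.** Define OS from the first radium-223 administration (C1D1) in protocol 8.3.2 and in SAP 7.2.1 and 7.5, as for PFS and time to first skeletal event. At the same time, align protocol 3.2, which describes progression as timed from inclusion, with the start-of-treatment origin in protocol 8.3.1 and SAP 7.1.1. SAP 8.5 needs no change on this account.

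If the sponsor prefers to keep inclusion as the origin, the alternative is to define its date and either analyse OS in all included patients or let patients enter the risk set at first dose (delayed entry).

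The cost of the main fix is wording. The first-dose date is already needed for PFS, so no new data are collected. Reported OS becomes shorter by the size of the gap.

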7.2. Reporting of AEs

AEs will be collected starting from the first procedure required by the study up to three months after patient's disease progression. Safety evaluation after progression will include follow-up of symptomatic skeletal related events until reach 2 years from the last dose of study treatment.

All study patients who experience AEs will be closely monitored during this time. All AEs should be recorded in the CRF.

All signs, symptoms, and results of procedures with abnormal diagnoses that are clearly related should be grouped together and reported as a single diagnosis or disorder wherever possible. Any other event that does not fulfill this definition will also be reported separately.

Reporting of SAEs and reporting period

Reporting requirements will comply with all applicable local regulations regarding safety reporting.

All SAEs and AESIs defined in the protocol will be reported to the Sponsor within a period of 24 hours from the time the investigator or any other member of the site staff becomes aware of the event, as follows:

- Regardless of the study drug received by the patient and whether or not the investigator considers this event to be related or not to the study drug, all SAEs and AESIs (as defined in this protocol), will be reported to MedSIR immediately, no later than 24 hours after any member of the study site staff becomes aware of the event.
- All information regarding the SAE and AESI should be obtained and recorded in full using the SAE form and sent to MedSIR.
- Follow-up information, copies of test results, event outcome and the opinion of the investigator as to the relationship between the IMP and the SAE and AESI, accompanied by other applicable documentation when it is requested, will be sent along with the SAE form, if available on the day the event is reported or as soon as possible if it is not.
- The original SAE reporting form of the Sponsor should be kept on file with the documentation from the CRF at the study site(s).

All SAE forms will be sent by the investigator or investigator staff to the Sponsor by e-mail and fax as indicated below:

E-mail: [contact]

Fax: [name]

Follow-up of the SAEs and AESIs will continue until they resolve, a stable outcome is reached, patient is lost to follow-up, or the patient dies.

MedSIR will be responsible for ensuring that events are reported to the European Medicine Agency (EMA), competent authorities, within the stipulated period, as needed.

AESIs

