 - 12. After end of treatment (if no progressive disease documented), efficacy follow-up visits will be performed every 3 months including radiological tumour assessments until disease progression.
 - 13. After disease progression, a safety follow-up visit will be performed within three following months and 24 months after last dose of treatment to evaluate symptomatic skeletal related events, overall survival and post-study anticancer therapy.

Appendix 2: Response Evaluation Criteria in Solid Tumors Guidelines (RECIST criteria) (version 1.1)

Eisenhauer, E.A., et al., *New response evaluation criteria in solid tumours: revised RECIST guideline (version 1.1)*. Eur J Cancer, 2009. 45(2): p. 228-47.

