#### 7.1.1 *Primary analysis*

The primary efficacy endpoint is the median PFS achieved with radium-223 treatment. The PFS will be evaluated at the first 34 months period of the study. The PFS will not be evaluated at the 2-years extension of the study for safety.

PFS is a composite endpoint defined as the time from the start of the radium-223 treatment to disease progression in bone or soft-tissue, symptoms, or death, according to the modified PCWG2 criteria.

Objective radiographic disease progression is defined as the presence of at least one of the following conditions:

- Bone lesion progression (appearance of  $\geq$  two new bone lesions compared to baseline).
- Soft-tissue lesion progression according to the RECIST criteria version 1.1.
- Presence of symptomatic skeletal events (pathological fractures, spinal cord compression, radiation or surgery to bone), which should have been reported as adverse event/serious adverse events.

Patients with no progression will be censored at the date of their last evaluation (see Table 1 – Appendix I).

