**Appendix I**

Table 1. Censoring rules for PFS

Situation	Date of progression or censoring	Outcome
Progression documented between scheduled visits	
Earliest of:
 

• Date of radiological assessment showing new lesion (if progression is based on new lesion); or

• Date of last radiological assessment of measured lesions (if progression is based on increase in sum of measured lesions); or

• Bone lesion progression (appearance of <math>\geq</math> two new bone lesions compared to baseline); or

• Presence of symptomatic skeletal events (pathological fractures, spinal cord compression, radiation or surgery to bone)

	Progressed
Death before first progression disease assessment	Date of death	Progressed
Death between adequate assessment visits	Date of death	Progressed
No progression	Date of last radiological assessment of measured lesions	Censored
Treatment discontinuation for undocumented progression	Date of last radiological assessment of measured lesions	Censored
Treatment discontinuation for toxicity or other reason	Date of last radiological assessment of measured lesions	Censored
Death or progression after more than one missed visit	Date of last radiological assessment of measured lesions	Censored

EudraCT number: 2016-001888-36

Table 2. Censoring rules for OS

Situation	End date	Status
Death during study follow-up	Date of death	Death
The patient is alive at last follow-up	Date of last follow-up	Censored

EudraCT number: 2016-001888-36

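### Time to first symptomatic skeletal event: the censoring date is undefined, and on the tumour-assessment reading, if later events still count, Kaplan-Meier risk is pushed upwards

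*SAP*

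**What the plan says.** SAP 7.2.1 and protocol 8.3.2 carry the same rule. Time runs from the start of treatment to the first SSE. If none has occurred when the analysis is done, or the patient is lost, "the time-to-event variables will be censored at the last disease assessment date". SAP 7.2 sets the horizon: "All efficacy endpoints will be evaluated at the first 34 months period of the study".

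Neither document says what a disease assessment is for this endpoint. The nearest texts are:

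- **SAP 8.5:** "patients without a date of disease progression will be analyzed as censored observations on the date of last tumor assessment". This covers only patients who have not progressed.
- **SAP Appendix I, PFS table:** "Date of last radiological assessment of measured lesions". The appendix has tables for PFS and OS but none for SSE.

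Tumour assessment and SSE capture stop at different times:

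- **Tumour assessment** (protocol Appendix 1, note 12): after treatment, "efficacy follow-up visits will be performed every 3 months including radiological tumour assessments until disease progression".
- **SSE source** (SAP 7.1.1): SSEs are events "which should have been reported as adverse event/serious adverse events".
- **AE collection** (protocol 7.2): "AEs will be collected starting from the first procedure required by the study up to three months after" the patient's progression. The same section continues SSE follow-up to 2 years after the last dose.
- **Contacts after progression** (Appendix 1, note 13): "a safety follow-up visit will be performed within three following months and 24 months after last dose of treatment".

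Protocol 3.6 ends the efficacy follow-up period at progression, death, withdrawal of consent or 34 months after the first inclusion, whichever is first. SAP 7.2.2 compares time to first SSE between AR-V7 cohorts by log-rank, but says outcomes are only described if very few AR-V7 patients are recruited.

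**The concern.** A Kaplan-Meier curve needs events and event-free time to be observed over the same period. Here the event side runs to the analysis. On the most natural reading of the undefined term, the event-free side stops at the last scan. A patient who progresses, has a fracture two months later and reports it counts as an event at the fracture date. A patient who progresses and is known to be fracture-free two months later leaves the risk set at the progression scan. Whether a patient's post-scan time is used then depends on whether he had the event.

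At stake are the SSE curve, its median and its confidence interval, and possibly the AR-V7 comparison of this endpoint. A patient who has progressed but is SSE-free has no censoring date fixed by any text, so two analysts could draw different curves from the same data.

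**Working it through.** The plan states no SSE figure to reproduce. The check is therefore one of direction (exact) and size (illustrative).

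**Direction.** The estimator is S(t) = product over event times of (1 − d/n), where d is the number of events and n the number at risk. Keep every event and its date, and move only the event-free censoring dates earlier. Each d is unchanged and each n can only shrink, so S(t) is equal or lower and risk equal or higher at every t. A check on 20,000 random datasets and 12,000 simulated trials found no violation.

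Example: 10 patients have SSEs at months 4, 10 and 16. The other seven are event-free, with last scan at month 6 and last SSE contact at month 20.

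- Last-scan rule: numbers at risk 10, 2, 1. S = 0.9, 0.9 × 1/2 = 0.45, then 0. Risk 10%, 55%, 100%.
- Censoring at month 20: numbers at risk 10, 9, 8. S = 0.9, 0.9 × 8/9 = 0.8, 0.8 × 7/8 = 0.7. Risk 10%, 20%, 30%.

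**Size: inputs.** From the documents: 23 months of accrual and 11 of follow-up (protocol 8.2), so follow-up is 34 minus uniform(0, 23) months; scans every 12 weeks to progression; target median PFS 6.3 months; AE collection to three months after progression. Assumed: exponential times; SSE median 18, 24 or 36 months; death median 14.9 months (the updated radium-223 arm in protocol 1.2) or 18.

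The 6.3-month target is for a composite that includes SSE and death, so radiographic progression was set in three ways. With ln2/6.3 = 0.110 per month:

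- **A:** 0.110 minus the SSE and death hazards (progression median 13.3 to 27.7 months). This matches the plan's composite.
- **B:** 0.110 minus the SSE hazard only (7.6 to 9.7).
- **C:** 0.110 for radiographic progression alone (6.3). This is the least consistent with the plan's composite.

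True 12-month event-free proportions are 2^(−12/18) = 0.630, 2^(−12/24) = 0.707 and 2^(−12/36) = 0.794.

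**Size: results.** Overstatement of 12-month SSE risk in percentage points, 400,000 patients per scenario, SSE capture to three months after progression:

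| Censoring date for event-free patients | A | B | C |
|---|---|---|---|
| Last scan, ending at the scan showing progression | 3.6–4.1 | 5.5–7.1 | 6.8–10.2 |
| Confirmatory scan six weeks later counts as the last assessment | 2.3–3.0 | 3.1–4.4 | 3.9–5.9 |
| Last scan if progressed, end of follow-up if not | 1.6–2.4 | 4.1–4.8 | 5.2–7.7 |
| Both softer conventions together | 0.8–1.2 | 2.1–2.4 | 2.5–3.9 |

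For example, under A with an SSE median of 18 months the estimate is 0.590 against 0.630, a difference of 4.0 points. A repeat run agreed with the table to within about 0.3 points. Censoring event-free patients at the end of the capture window returned the true value within 0.2 points in every scenario. So did not counting events after the last scan, within about 0.3. About 8 to 18 first SSEs would be counted in 52 patients.

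**AR-V7 comparison.** Under A, with equal true SSE and death hazards and three-month capture, the apparent hazard ratio is 1.23–1.25 if composite PFS medians are 3 and 6.3 months, 1.08–1.10 if 4.5 and 6.3, and 1.00 with matched windows. With 13 versus 39 patients and medians of 3 and 6.3, a two-sided 5% log-rank test rejects in 7–8% of trials, against 4–5% when matched.

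**The case against.** The strongest reply is that the documents already contain a benign reading. Time to first SSE is listed as an efficacy endpoint, protocol 3.6 ends efficacy follow-up at progression, and SSE follow-up after progression is labelled safety evaluation. Read together, later SSEs are safety data and the mismatch goes away. This stands as real support for that reading. It does not settle the matter, because SAP 7.2.1 tests whether an event has occurred by the time of the analysis and does not limit counting to efficacy follow-up. Equally, nothing prevents an analyst from treating an SSE contact as a disease assessment, which would also remove the problem.

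Second, the size may be small. Protocol 5.2 and Appendix 1 note 8 require a confirmatory bone scan at least six weeks later (protocol 3.2 limits this to the first reassessment), and every patient has bone metastases, so that scan may well be the last assessment. With unprogressed patients also followed to the end, the overstatement is about 1 to 4 points. With 52 patients and a risk near 29%, the standard error is at least √(0.29 × 0.71/52) = 6.3 points. This stands as to size. But the error is systematic and goes one way, and larger samples would not reduce it.

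Third, on AR-V7, the protocol hypothesises equal efficacy in the two cohorts, only about 13 positive patients are expected, and the SAP falls back to description if there are very few. This stands as a limit on the consequence.

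**Conclusion.** The point holds in conditional form. The censoring date is undefined, and for a progressed, SSE-free patient no text supplies it. If it means the last tumour assessment and later SSEs are counted, Kaplan-Meier SSE risk is equal to or higher than with the same events and event-free patients censored at the end of SSE capture. That direction is algebraic. The size is not: about 1 to 10 points at 12 months across the assumed rates and conventions, and about 1 to 4 under the mildest combination, all with capture to three months after progression.

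A reader might infer more than the documents support:

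- **That the SSE curve will certainly be biased.** It will not if later SSEs are left out or SSE contacts count as assessments.
- **That risk is higher than under any consistent rule.** If events are also cut at the last scan, the inequality can fail at some times. Take an SSE at month 10 after a last scan at month 3, an SSE at month 6, and one patient event-free at month 12. Risk at month 6 is 33% under the last-scan rule but 50% when events are truncated; from month 10 it is 67% against 50%.
- **That the larger figures for complete SSE capture to month 34 apply** (about 5 to 13 points). Scheduled contacts after progression are too sparse to rely on that.
- **That the AR-V7 comparison is distorted.** This needs the cohorts to progress at different speeds and the comparison to be formally tested.
- **That the primary result is at risk.** The primary PFS test and the sample size of 52 are untouched.

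This merits correction before analysis, as a secondary-endpoint matter.

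**What to change.** In SAP 7.2.1 and protocol 8.3.2, define one SSE observation window per patient whose end does not depend on whether an SSE occurred. An example is the earliest of:

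- death;
- the 34-month cut-off;
- withdrawal or loss to follow-up;
- either the last tumour assessment or the end of AE collection three months after progression, with one of the two chosen and stated.

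Count SSEs only up to that date, and censor event-free patients at that same date.

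Two details matter. An unscheduled SSE report must not by itself extend the window: if it counts as an ascertaining contact, about 1 to 3.5 points of bias remain, whereas a window end set independently of SSE occurrence returns the true value within about 0.3. And because SAP 7.1.1 treats an SSE as a progression event, a window ending at the last tumour assessment must not be closed by the SSE itself, or that event would fall outside its own window.

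The cost is wording in two places, with no new patients, visits or analyses. The window end date must be derivable from the database, and SSEs after the window would be reported as safety data only.
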